5.4. Examination of Covariates and Other Strata

5.4.1. Covariates and Other Strata

- Randomization is stratified by **long-acting bronchodilator** usage during the run-in (none or one **long-acting bronchodilator** per day) and long-acting bronchodilator usage will be included as a covariate in all statistical models. The no. of bronchodilators per day during run-in be re-derived and used for analysis. The randomized stratum from RAMOS and reported on the eCRF will be listed only.
- Other covariates will be included for specific analyses as detailed in model specifications in Section 7 and Section 8.

5.5. Multiple Comparisons and Multiplicity

See Section 2.4 for details on inferences that can be drawn on primary, secondary and 'other' endpoints.

5.6. Other Considerations for Data Analyses and Data Handling Conventions

Other considerations for data analyses and data handling conventions are outlined in the appendices:

Section	Component
10.2	Appendix 2: Assessment Windows
10.3	Appendix 3: Study Phases and Treatment Emergent Adverse Events
10.4	Appendix 4: Data Display Standards & Handling Conventions
10.5	Appendix 5: Derived and Transformed Data
10.6	Appendix 6: Reporting Standards for Missing Data

6. STUDY POPULATION ANALYSES

6.1. Overview of Planned Study Population Analyses

The study population analyses will be based on the ITT population, unless otherwise specified.

Study population analyses including analyses of subject's disposition, protocol deviations, demographic and baseline characteristics, prior and concomitant medications, and treatment compliance will be based on GSK Core Data Standards. Details of the planned displays are presented in [Appendix 8: List of Data Displays](#)

6.1.1. Disposition

The study population summary will show the number of subjects overall who were enrolled, the number of pre-screen failures, the number of screen failures and the number with each reason for screen failure, the number of run-in failures each reason the number with each reason for run-in failure and the number of subjects in each treatment group and overall who were randomized, in the ITT population. Of those in the ITT population the number and percentage of subjects in the AM population will be presented by treatment and overall.

The end of study record summary shows the number of subjects who completed the study as well as the number who withdrew early from the study along with reasons for early withdrawal.

The summary of study treatment status shows the number of subjects who completed study treatment as well as the number who stopped study treatment prior to the end of the study, along with the reasons for discontinuation.

6.1.2. Medical Conditions

The number and percentage of subjects reporting each current medical condition will be presented by randomized treatment group and overall. All medical conditions must be summarised on this table regardless of frequency.

This will be repeated for past medical conditions.

6.1.3. Concomitant Medications

Medications that have been stopped prior to Screening will be listed and not be included in any summary tables.

Medications not taken for an exacerbation will be summarised by Anatomical-Therapeutic-Chemical (ATC) level 1 and ingredient. COPD medications given for an exacerbation will be summarised by Respiratory Medication Class (RMC).

Medications taken for an exacerbation and those not taken for an exacerbation will be listed separately. Both listings will indicate in which study phases each medication was taken (pre-treatment and/or on- treatment and/or post-treatment)

6.1.4. Screening Lung Function Tests

Pre- and post-salbutamol FEV₁, FVC and FEV₁/FVC ratio, post-salbutamol FEV₁ as a percentage of predicted normal and FEV₁ reversibility to salbutamol (expressed in mL and as a percentage) at Screening will be summarised by treatment group and overall.

6.1.5. GOLD Grade/Categories, Reversibility and long-acting bronchodilator usage Stratum

The number and percentage of subjects in each GOLD Grade 1-4 and GOLD Category A-D using CAT, the number and percentage of subjects classified as Reversible/Non-reversible to salbutamol at Screening and the number and percentage of subjects in each stratum (none or one long-acting bronchodilators per day) based on the long-acting bronchodilator usage during run-in (all defined in Section 10.5.2) will be presented by treatment group and overall.

6.1.6. Maintenance Naive

Summary Maintenance Naive and Non-Maintenance Naive status will be presented by treatment group and overall.

7. PRIMARY STATISTICAL ANALYSES

7.1. Primary Efficacy Analyses

7.1.1. Endpoint / Variables

Trough FEV₁ at Week 24

7.1.2. Summary Measure

Mean change from baseline

7.1.3. Population of Interest

The primary efficacy analyses will be based on the ITT population,.

7.1.4. Strategy for Intercurrent (Post-Randomization) Events

An intercurrent event considered to have an impact on the estimand for the ITT population analysis is:

- Discontinuation of randomised treatment

- The primary treatment effect to be estimated for the ITT population will be the hypothetical effect if all subjects had stayed on their randomised treatment.

7.1.5. Statistical Analyses / Methods

Details of the planned displays are provided in [Appendix 8: List of Data Displays](#) and will be based on GSK data standards and statistical principles.

Unless otherwise specified, endpoints / variables defined in Section [7.1.1](#) will be summarised using descriptive statistics, graphically presented (where appropriate) and listed.

7.1.5.1. Statistical Methodology Specification

Primary Statistical Analysis
Endpoint

 • Change from Baseline in trough FEV₁ at Week 24 (results for trough FEV₁ at all other time points and other treatment comparisons will be obtained from the same analysis even though those are not the primary endpoint)
Model Specification

 • Trough FEV₁ at Week 24 will be analysed for the ITT population using a mixed model repeated measures (MMRM) including data recorded at each of Week 4, Week 12 and Week 24. • The following covariates will be included in the model: baseline FEV₁, geographical region, stratum (no. of bronchodilators per day during run-in), visit, treatment, visit by baseline and visit by treatment interactions, where visit is nominal. • Two models will be fitted; one with a response variable of trough FEV₁, and one with a response variable of change from baseline in trough FEV₁. • While missing data are not explicitly imputed in the primary MMRM analyses, there is an underlying assumption that the data are missing at random. • The Kenward and Roger method (KR) for approximating the denominator degrees of freedom and correcting for bias in the estimated variance-covariance of the fixed effects will be used. • In the event the model fails to run using the KR method, then the residual method will be used instead. • An unstructured covariance structure for the R matrix will be used by specifying 'type='UN' on the REPEATED line. • Results for all time points where data are scheduled to be collected and all treatment comparisons will be included in the analysis and presented in the displays.
Model Checking & Diagnostics

 • Model assumptions will be applied but appropriate adjustments may be made based on the data.

Primary Statistical Analysis

- Normality assumptions underlying the model used for analysis will be examined by obtaining a normal probability plot of the residuals and a plot of the residuals versus the fitted values (i.e. checking the normality assumption and constant variance assumption of the model respectively) to gain confidence that the model assumptions are reasonable.
- If there are any departures from the distributional assumptions, alternative models will be explored using appropriately transformed data.

Model Results Presentation

- Least squares (LS) mean and LS mean changes from baseline with their corresponding standard errors (SEs) will be presented for each treatment by visit, together with estimated treatment differences (UMEC/VI 62.5/25 vs. UMEC 62.5, UMEC/VI 62.5/25 vs Salmeterol and UMEC 62.5 vs Salmeterol), corresponding 95% CIs and p-values.
- A plot of LS mean changes from baseline and 95% CIs for each treatment by visit will be generated.
- A plot of LS mean treatment differences and 95% CIs between the treatment groups by visit will also be generated.
- The type III tests of fixed effects and the covariance parameter estimates from the model will be presented in two tables.

Summary Results Presentation

- Summary of baseline FEV₁ will be presented by treatment for all subjects.
- A box plot and an empirical distribution function plot of change from baseline in trough FEV₁ at Week 24 will be produced.
- Summary statistics for raw and change from baseline in trough FEV₁ at each visit and for each treatment will be presented on the same table.

Sensitivity and Support Statistical Analysis

- An assessment of whether the effect of treatment is modified by the interaction with
 - o Baseline FEV₁
 - o Geographical Region
 - o Stratum (no. of bronchodilators per day during run-in)
 will be made (for primary endpoint only for the ITT population only) by fitting separate MMRM models including an additional term for treatment by each covariate. The interaction term will be tested at the 10% significance level.
- For factors with two levels or continuous factors i.e. Baseline FEV₁ and Stratum, interactions with treatment will be investigated by fitting a model with the same terms as the main model, and adding in treatment by factor by Visit interaction. Contrast statements will be used to obtain the p-value for the treatment by factor interaction at Week 24. If that p-value is ≥ 0.10 the interaction will be considered not significant. If the p-value is < 0.10 , further investigation will be performed, for example running analysis by each level of the factor, or for subgroups

above and below the median.

- For factors with more than 2 levels i.e. Geographical Region, the overall interaction of factor by treatment will be investigated by fitting a model with the same terms as the main model, and adding in treatment by factor interaction. The p-value for the overall treatment by factor interaction will be obtained. If that p-value is ≥ 0.10 the interaction will be considered not significant. If the p-value is < 0.10 then the analysis will be repeated including the treatment by factor by visit interaction and the p-value for the interaction on Week 24 obtained. If that p-value is ≥ 0.10 the interaction will be considered not significant. If the p-value is < 0.10 then the factor will be dichotomised – for example US vs. non-US and EU vs. non-EU for geographical region interactions (several different dichotomies may be explored). A model will be fitted with the same terms as the main model, and adding in treatment by dichotomized factor by Visit interaction, and contrast statements will be used to obtain the p-value for the treatment by dichotomized factor interaction on Week 24. If that p-value is ≥ 0.10 the interaction will be considered not significant. If the p-value is < 0.10 , further investigation will be performed, for example running analysis by each level of the factor.

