5.2. Baseline Definitions

For all endpoints (except as noted in baseline definitions) the baseline value will be the latest pre-dose assessment with a non-missing value, including those from unscheduled visits. If time is not collected, Day 1 assessments are assumed to be taken prior to first dose and used as baseline.

Endpoint	Baseline derivation
Trough FEV ₁ , FVC and IC	The mean of the values measured at 30 min and 5 min pre-dose on Day 1. If the actual time of an assessment is after the time of dosing on Day 1, the value at that assessment will be

Endpoint	Baseline derivation
	
set to missing prior to calculating baseline.
 
If one of the values is missing then the baseline will be the single remaining value; otherwise the baseline will be the mean of the two values.

TDI	
BDI assessment taken prior to dosing on Day 1.
 
The baseline dyspnea index (BDI) focal score will be calculated as the sum of the ratings recorded for each of the three individual scales (Functional Impairment, Magnitude of Task, Magnitude of Effort). Each of these scales has five possible scores ranging from 0 to 4 (with lower scores indicating more impairment), so the range of the BDI focal score is 0 to 12. If a score is missing (or has a value of W, X or Y) for any of the three scales, then the BDI focal score will be set to missing.

E-RS and subscale scores	Average of measurements from day -28 to day -1 inclusive; at least 16 days must be non-missing.
Physical activity	Average of measurements prior to randomisation; at least 3 days must be non-missing.
Rescue Use - Mean Number of Puffs of Rescue Medication Per Day and Percentage of Rescue-free Days Over Weeks 1-24 captured using e-diary	
The total puffs of rescue for each day will be calculated as number of salbutamol puffs. If the number of puffs is missing then the total puffs will be set to missing for that day.
 
The baseline number of inhalations is calculated using the mean number of total inhalations and the baseline percentage rescue use is calculated from the percentage of rescue free days as the average of measurements from day -28 to day -1 inclusive; at least 14 days must be non-missing.

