
 • Ratio of trough FEV1 to baseline FEV1 at Week 24 will be analysed for the ITT population using a mixed model repeated measures (MMRM) including data recorded at each of Week 4, Week 12 and Week 24. The model will have a response of log (Trough FEV1/Baseline FEV1) with covariates of log (baseline FEV1), geographical region, stratum (no. of bronchodilators per day during run-in), visit, treatment, visit by log (baseline FEV1) and visit by treatment interactions, where visit is nominal. Results will be back transformed to provide point estimates for the ratios. • Trough FVC and Trough IC endpoints above will be analyzed using the same methodology as the primary analysis of trough FEV1 (detailed in Section 7.1) using all available FVC or IC data recorded at Weeks 4, 12 and 24 and with relevant baseline. Baseline defined in Section 5.2. 
The following will apply for all the endpoints FEV1, FVC and IC:
 
 • The Kenward and Roger method (KR) for approximating the denominator degrees of freedom and correcting for bias in the estimated variance-covariance of the fixed effects will be used. • In the event the model fails to run using the KR method, then the residual method will be used instead. • An unstructured covariance structure for the R matrix will be used by specifying 'type='UN' on the REPEATED line.
Model Checking & Diagnostics

 • Model assumptions will be applied but appropriate adjustments may be made based on the data. • Normality assumptions underlying the model used for analysis will be examined by obtaining a normal probability plot of the residuals and a plot of the residuals versus the fitted values (i.e. checking the normality assumption and constant variance assumption of the model respectively) to gain confidence that the model assumptions are reasonable. • If there are any departures from the distributional assumptions, alternative models will be explored using appropriate transformed data.
Model Results Presentation

 • Least squares (LS) mean and LS mean changes from baseline with their corresponding

Secondary Statistical Analysis

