10. APPENDICES

10.1. Appendix 1: Schedule of Activities

10.1.1. Protocol Defined Schedule of Events

			Blinded Treatment					
Visit	Pre-screen ¹ 0	Screen/ Run-in 1	Rando- mization 2	3	4	5	EW Visit ²	Telephone Follow up contact 6
Week	-10 to -4	-4	0	4	12	24		
Day	-70 to -28	-28	1	28	84	168		7 days after V5 or EW Visit
Window	-7/+2 days	-7/+2 days	-7/+2 days	-7/+2 days	-7/+2 days	-7/+2 days		±3 days
Screen/Baseline								
Informed consent	X							
Demography	X							
Medical/COPD history		X						
Smoking history/status		X						
Smoking cessation counselling		X						
Concomitant medication assessment	X	X	X	X	X	X	X	X
Height and weight		X						
Cardiovascular History/family history of premature CV disease)		X						
Screening spirometry (including post bronchodilator testing) ³		X						
CAT questionnaire		X	X					
Verify Inclusion/Exclusion Criteria		X						
Training on use of inhalers		X	X					
Training on use of eDiary and eMDI		X	X					
Verify randomization Criteria			X					

			Blinded Treatment					
Visit	Pre-screen ¹ 0	Screen/ Run-in 1	Rando- mization 2	3	4	5	EW Visit ²	Telephone Follow up contact 6
Week	-10 to -4	-4	0	4	12	24		
Day	-70 to -28	-28	1	28	84	168		7 days after V5 or EW Visit
Window	-7/+2 days	-7/+2 days	-7/+2 days	-7/+2 days	-7/+2 days	-7/+2 days		±3 days
Register Visit in InForm	X	X	X	X	X	X	X	X
Register Visit in RAMOS NG	X	X	X	X	X	X	X	X
Efficacy/HRQoL assessments								
Spirometry, including pre-dose FEV ₁ , trough FEV ₁ and inspiratory capacity			X	X	X	X		
SAC BDI questionnaire ⁴			X					
SAC TDI questionnaire ⁴				X	X	X		
SGRQ-C questionnaire ⁴			X	X	X	X		
CAT questionnaire ⁴		X	X	X	X	X		
EXACT/ER-S: COPD ⁵		—————→						
Patient Global Rating of COPD severity			X	X	X	X		
Patient Global Rating of Change in COPD				X	X	X		
Safety assessments								
Adverse events/Serious adverse events ⁶	X	X	X	X	X	X	X	X
COPD exacerbation assessment	X	X	X	X	X	X	X	X
12-Lead ECG		X						
Urine pregnancy test ⁷		X	X			X	X	
Pharmacogenetic sample ⁸			←———— X —————→					
Medication/Supplies								
Dispense rescue albuterol/slabutamol. Dispense MDI ⁹		X	X	X	X	X		
Assess COPD medication compliance ¹⁰ during run-in			X					
Dispense eDiary		X						
Assess compliance with eDiary during run-in			X					
Collect rescue albuterol/slabutamol.			X	X	X	X	X	

			Blinded Treatment					
Visit	Pre-screen ¹ 0	Screen/ Run-in 1	Rando- mization 2	3	4	5	EW Visit ²	Telephone Follow up contact 6
Week	-10 to -4	-4	0	4	12	24		

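### The primary trough FEV₁ model adjusts for one pre-treatment occasion only; adding the screening FEV₁ is a nearly free improvement that may gain precision, but nothing in the plan is wrong

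*SAP*

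**What the plan says.** SAP section 7.1.5.1 fits trough FEV₁ at Weeks 4, 12 and 24 in an MMRM. Its list of terms begins: "The following covariates will be included in the model: baseline FEV₁, geographical region, stratum". The remaining terms are the visit and treatment effects, with baseline and treatment each allowed to interact with visit. No other lung function measure is adjusted for.

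Section 5.2 defines the baseline for FEV₁, FVC and IC: "The mean of the values measured at 30 min and 5 min pre-dose on Day 1". If only one of the two exists, that one is used: "If one of the values is missing then the baseline will be the single remaining value". Screening spirometry plays no part.

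The schedule in section 10.1.1 has a Visit 1 (Week -4) row that reads "Screening spirometry (including post bronchodilator testing". Section 6.1.4 plans to summarise "Pre- and post-salbutamol FEV₁, FVC and FEV₁/FVC ratio, post-salbutamol FEV₁ as a percentage of predicted normal". Section 10.5.2 uses the screening values for the reversibility class and GOLD grade. They are put to no other analytic use.

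In section 7.2.5.1 the FEV₁ ratio model adjusts for log baseline FEV₁ only. FVC and IC follow the primary method, "using all available FVC or IC data recorded at Weeks 4, 12 and 24 and with relevant baseline". CAT is scheduled at Visits 1 and 2. Under the general rule of section 5.2, which takes the latest pre-dose value, the Visit 2 score is the baseline wherever it is present.

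**The concern.** Averaging two readings taken 25 minutes apart reduces within-session error. It does not reduce day-to-day variation, which both readings share. A pre-bronchodilator FEV₁ from four weeks earlier is a second look at the patient's underlying level. A post-salbutamol FEV₁ reflects bronchodilator responsiveness, which could plausibly relate to outcome when all three arms are bronchodilators. Both values precede randomisation, so adjusting for them cannot bias the treatment contrast.

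What is at stake is the width of the interval for UMEC/VI versus UMEC. That comparison gates all further inference under section 2.4. The same applies to the two salmeterol contrasts, the ratio and FVC models, and the maintenance-naive analyses, which section 7.4 fits separately within each subgroup and so on fewer patients.

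**Working it through.** **What the SAP gives.** Section 2.3 gives 3232 screened, 2424 randomised 1:1:1 and about 2181 evaluable. The counts agree with each other: 3232 × 0.75 = 2424, and 727/0.90 = 807.8, rounded up to 808 per arm, × 3 = 2424. The 25% and 10% are inferred from the counts. The SAP states no effect size, SD, power or between-occasion correlation, so it contains no precision figure to reproduce. Every correlation below is an assumption.

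**Formula.** Let b be the correlation of Day 1 with Week 24 FEV₁, s that of screening with Week 24, and k that of screening with Day 1.

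- Residual variance share with Day 1 only: 1 − b².
- With both occasions: 1 − (b² + s² − 2·s·b·k)/(1 − k²).
- The proportional cut equals the squared partial correlation, p², where p = (s − b·k)/√[(1 − b²)(1 − k²)].
- The standard error falls by 1 − √(1 − p²).

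This treats Week 24 in isolation and ignores region, stratum and the earlier visits, so it approximates the MMRM contrast.

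**One case in full.** With k = 0.90, b = 0.87, s = 0.85:

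- Day 1 only: 1 − 0.7569 = 0.2431.
- Both: 1 − (0.7569 + 0.7225 − 1.3311)/0.19 = 0.2195.
- Cut: 1 − 0.2195/0.2431 = 9.7%; standard error 5.0% smaller.

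**Other cases**

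| k | b | s | variance cut |
|---|---|---|---|
| 0.88 | 0.90 | 0.90 | 27.2% |
| 0.90 | 0.87 | 0.87 | 16.4% |
| 0.90 | 0.87 | 0.83 | 4.8% |
| 0.92 | 0.88 | 0.84 | 2.7% |
| 0.92 | 0.88 | 0.83 | 1.2% |
| 0.93 | 0.90 | 0.85 | 0.7% |
| 0.95 | 0.90 | 0.85 | 0.1% |

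**Whole range.** Take k from 0.88 to 0.95, b from 0.85 to 0.90, and s from b − 0.05 to b, in steps of 0.01. That gives 8 × 6 × 6 = 288 combinations. The cut runs from about 0% to 27%, with a median of 6.6%. In 77 of the 288 (27%) it is below 3%. At the median the standard error is 1 − √0.934 = 3.4% smaller, equivalent to 2424/0.934 − 2424, or about 171 further patients.

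**Two reference patterns.** If all three occasions were equally correlated at r, the variance ratio would be (1 + 2r)/(1 + r)². For r = 0.7, 0.8 and 0.9 this is 0.830, 0.802 and 0.776, a cut of 17–22%. If correlation simply decays along the sequence, s = b·k, so p = 0 and the cut is 0%.

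**CAT.** Assume k = 0.75–0.80, b = 0.55–0.60 and s = 0.50–0.60, with s no larger than b. The top is (0.75, 0.60, 0.60): p = 0.15/√(0.64 × 0.4375) = 0.283, a cut of 8.0%. The bottom is (0.80, 0.60, 0.50): p = 0.02/0.48 = 0.042, a cut of 0.2%. The range is therefore about 0–8%.

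**Post-salbutamol FEV₁.** No figure can be offered for its increment without its correlations with the other three measurements.

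**The case against.** The planned model is a sound standard choice. Under the assumed b of 0.85–0.90, Day 1 baseline alone already explains b² = 72–81% of the outcome variance, and no shortfall in precision is shown with 2424 randomised. Day 1 closes the run-in and is nearer in time to Week 24. Screening precedes four weeks on none or one long-acting bronchodilator, so its conditions may differ. Both features favour a lower screening–Week 24 correlation, where the gain shrinks. Post-salbutamol FEV₁ is probably close to the pre-salbutamol value from the same visit and may add little. All of this stands, and it is why the point is an optional improvement.

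A reader might go further and infer that the planned standard errors are certainly wider than the collected data allow, or that some minimum saving is assured. The documents support neither. Any gain needs a non-zero partial correlation of screening FEV₁ with Week 24 given Day 1, and the SAP contains nothing from which to estimate it.

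What does not stand is that a possibly small gain makes the change pointless. The values are already scheduled at Visit 1. Two covariates with visit interactions cost negligible degrees of freedom at this sample size. Collinearity between screening and Day 1 FEV₁ does not harm the treatment contrast.

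**Conclusion.** The point holds as a missed opportunity. One pre-treatment FEV₁ occasion is in the model, and a second is scheduled for all subjects but unused in every trough model. The planned analysis is valid; its estimand and type I error are not in question.

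Under the assumed correlations, screening pre-salbutamol FEV₁ lowers residual variance by about 0–27%, with a median of about 6.6%. That median describes the assumed grid and is not an estimate for this trial. It would be wrong to read into it a guaranteed floor, a definite extra gain from post-salbutamol FEV₁, or a benefit to every FEV₁-based result: the time-to-deterioration models with an FEV₁ component lie outside both the calculation and the change proposed. The CAT gain is about 0–8% under its own assumptions and is secondary.

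**What to change.** Amend SAP section 7.1.5.1 and the matching parts of 7.2.5.1 before unblinding:

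- **Primary trough FEV₁ MMRM:** add screening pre-salbutamol FEV₁ and, as a separate covariate, screening post-salbutamol FEV₁, each with its visit interaction. Do not average the post-salbutamol value into baseline, since it is measured under different conditions.
- **FEV₁ ratio model:** add the same terms on the log scale.
- **FVC model:** add screening FVC with its visit interaction.
- **CAT model (optional):** add the Visit 1 CAT score with its visit interaction.
- **Unchanged:** the Day 1 baseline, the definition of change, the estimand and the significance level.
- **Missing screening values:** replace with the overall mean across all arms, on the scale used in the model, so that no subject is lost.

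The cost is SAP wording and one or two extra covariates per model, with no new data collection. Fixing the terms in advance matters, because section 7.1.5.1 leaves room for data-based model adjustments, and adding covariates by that route after unblinding would be hard to defend.
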